complete the survey, which assesses the dimensions of engagement, safety, and environment once annually at the end of each academic year for the four years of intervention vs. comparison (2019-20, 2020-21, 2021-22, 2022-23). Due to the COVID-19 pandemic, the team was unable to collect SCS data from students in [REDACTED] schools during the first academic year (2019-2020). While this means a compromised set of Year 1 data on school climate for the [REDACTED] site, such measurement is intact for SC, and we will still be able to document trends in time in school climate in [REDACTED] for years 2-4 of the intervention vs. comparison period. Additionally, the study team will collect rosters of classrooms receiving The Guide Curriculum (GC). This will enable two sets of analyses: first, we will document which students receiving Tier 3 services and participating fully in the study are exposed to GC and account for this in terms of interventions received in analyses. Second, this will significantly expand a second level of enrollment for the study, as we will have de-identified academic records for all students (related to recently approved amendments), and will explore impacts of the GC on academic record variables (e.g., discipline problems, grades, attendance) for students in classrooms in Partnership schools receiving it compared to students in demographically comparable classrooms from Wellness schools that do not receive it.

The second stream of data collection will focus on students receiving Tier 3 services and consenting to be in the study. Clinicians will collect these measures with students and families at intake, every three months, and at case closure, using an electronic data portal coordinated by [name] and the Informatics Team at the Medical University of South Carolina (MUSC). The measurement strategy for each of the study aims is presented here:

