**Analytic Plan.** The proposed project is a cluster-randomized controlled trial (J=22 schools; 11 per treatment arm) comparing the efficacy of Wellness vs. Partnership services. As a general analytic plan, we will use hierarchical linear modeling (HLM) to evaluate the project aims. Specifically, we will use two-level HLM models to account for students being nested within schools. Though one might conceptualize this proposal as a three-level model (i.e., students nested within schools, and schools nested within sites), it would be neither feasible nor recommended to model site as a multilevel variable given there are only two sites in the design (56). In line with best practice, we will integrate site (i.e., SC vs. MD) as a covariate in the statistical models to contain any potential effects of this variable. Based on prior research conducted by the team, we expect intraclass correlations (ICCs) to warrant the incorporation of random intercepts to account for violations of independence. We will also test independence assumptions for the treatment parameters to determine how sensitive treatment effects are to potential violations of independence, and will include random slopes to account for nested treatment effects if ICCs exceed .01. For transparency, we will report both fixed and random effects (i.e. intercepts and slopes) of the model. Additionally, we will iteratively subset the model using a k-1 sensitivity analysis to determine the influence of individual sites on parameter estimates. We will estimate statistical models using full information maximum likelihood to accommodate any missing data (57). We will use maximum likelihood with robust standard errors to estimate models that include the Zero Inflated Poisson link function for count

PRINCIPAL INVESTIGATOR: [name]

outcomes (e.g. absences, referrals). This general analytic framework will be used in aims 1 and 2. Details, exceptions, and modifications to it are discussed below.

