In addition to primary intent to treat analyses, we plan to use quasi-experimental methods to test dose-response, and treatment engagement on a core aspect of the Partnership Condition – the mental health literacy intervention through the program, The Guide. In Partnership schools, this intervention has continued to be implemented through all phases of the pandemic, going from virtual in some phases to in-person in classrooms. We are able to access student academic records (demographics, grades, attendance, discipline) for students in Partnership classrooms receiving The Guide, as well as students in comparable wellness classrooms not receiving it. Per below, we have a large sample size to pursue these supplementary analyses. In these analyses, we will be overpowered (MDES below .1) to understand the impact of this mental health literacy intervention on student functioning, including examining dose of intervention given variability in teachers' delivery of it. We also have broader school climate data to explore the impact of the Partnership intervention on this variable (collected fall, 2019; fall, 2020; fall, 2021; spring, 2022; and spring, 2023).

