*Study retention.* Due to documented accessibility advantages of SBH (16) and our past experiences, Tier 3 students and parents are likely to remain involved in the study throughout the span of treatment. Additionally, the intervention requires no extra effort to participate outside of the assessments, with similar types of assessments routinely used in treatment for progress monitoring. In similar studies conducted, the most common reason for study attrition was due to students transferring to another school, which has been nominal across school wide populations. However, Tier 3 students experiencing EB problems are more likely to transfer schools than the general population.

*Incorporating research activities into routine care.* All research activities will be included in routine SBH functions. Consent to participate will be integrated into the existing process that clinicians use to obtain consent for treatment. Students and their parents may notice that their clinician is utilizing some new strategies, however all within parameters of expected clinical care. The same is true in the Partnership condition, will all enhancements those that would logically occur in a school embracing innovation and pursuing holistic strategies to remove barriers to student learning.

*Training and experience of recruitment personnel.* For students receiving Tier 3 services, the 20 clinicians will assist in study recruitment. Beginning in Year 2, a clinician was added in two [REDACTED] schools, one per condition for a total of 22 clinicians. Beginning in Year 3, two additional schools were added, one per condition, for a total of 22 schools and 24 clinicians. All clinicians will have a master's degree in a behavioral health discipline (e.g., psychology, counseling, social work) and will hold a valid license to provide psychological services or be under the supervision of a licensed clinician. Each clinician will participate in human subjects training prior to recruitment efforts and will be trained by the research team on recruitment procedures. The Lead Research Manager, [name], will oversee recruitment efforts with the PI, [name] and Co-I/MD Site PI, [name], as guided by the SAB and building on experiences from prior RCTs conducted

PRINCIPAL INVESTIGATOR: [name]

by the research team, including a large current RCT funded by the National Institute of Justice that includes an opt-out procedure. See below for recruitment parameters.

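### The Guide analyses are called overpowered (MDES below .1) on student numbers alone, which cannot deliver that figure for a contrast between at most 22 schools

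*Combined protocol and SAP*

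**What the plan says.** The Analytic Plan adds quasi-experimental analyses of The Guide, the mental health literacy component, to the primary intent-to-treat analyses. It gives the basis for their power as "Per below, we have a large sample size to pursue these supplementary analyses" and then states: "In these analyses, we will be overpowered (MDES below .1) to understand the impact of this mental health literacy intervention on student functioning". The same sentence goes on to include the dose of The Guide that teachers delivered.

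The Measures and Measurement Plan defines the comparison as "students in classrooms in Partnership schools receiving it compared to students in demographically comparable classrooms from Wellness schools that do not receive it". It says of collecting these records that "this will significantly expand a second level of enrollment for the study".

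The Analytic Plan describes 22 schools, 11 per arm, analysed with two-level models of students within schools. It says "we expect intraclass correlations (ICCs) to warrant the incorporation of random intercepts to account for violations of independence", without giving a value. The paragraph on recruitment personnel records that, from Year 3, "two additional schools were added, one per condition, for a total of 22 schools and 24 clinicians", so there were 20 schools before then.

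The Power considerations give an MDES of .29 for N=1225 and .28 for N=1400, at 80% power with 30% of variance explained by pre-test covariates. Those figures are for the primary outcomes, not for The Guide. Neither alpha nor an ICC is stated.

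**The concern.** Whether a class receives The Guide depends on the arm of its school, so the main contrast is between schools. In such a contrast the sampling variance has a part that shrinks with the number of students and a part that shrinks only with the number of schools. A large student sample removes the first part and leaves the second. An MDES below .1 would then rest on a very small ICC or a very high school-level R², and the plan offers neither as its reason.

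What is at stake is how a null result would be read. A reader told that these analyses are overpowered could take a null finding on The Guide as ruling out effects near .1. The plan has not shown that 22 schools can detect such effects.

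**Working it through.** **Inputs**

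| Quantity | Value | Source |
|---|---|---|
| Schools, J | 22, equal arms (20 before Year 3) | Analytic Plan; recruitment personnel paragraph |
| Students per school, n | 600 as a generous case; also unlimited | Recruitment Plan (average school population) |
| Power | 80% | Power considerations; carried over, as an assumption, from the primary outcomes |
| Student-level R² | .30 | Same source, same assumption; the plan does not say at which level the 30% applies |
| Alpha | two-sided .05 | Assumed; not stated |
| ICC (ρ), school-level R² | not stated | Shown as a range |

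**Formula** (standardised mean difference, two-level model, equal allocation):

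MDES = M × √{ (4/J) × [ ρ(1 − R²_school) + (1 − ρ)(1 − R²_student)/n ] }

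with M = t.975 + t.80 on J − 2 df. For J = 22: M = 2.086 + 0.860 = 2.946.

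**Can the plan's figure be reproduced?** No, because its inputs are not given. If clustering were ignored, an MDES of .10 would need 4 × (1.960 + 0.842)² / .01 ≈ 3,140 students in total, or about 2,198 with 30% of variance explained. A student-level calculation on a large sample would therefore give a figure below .1. That the plan did this is an inference only.

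**Does the formula fit the plan's other figures?** Yes. With R² = .30 at both levels and ρ = .0577, it gives .287 at n = 1225/22 = 55.7 and .283 at n = 1400/22 = 63.6, which round to the stated .29 and .28.

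**Best case, unlimited students.** The second term vanishes, so MDES < .10 requires

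ρ(1 − R²_school) < .01 × 22 / (4 × 2.946²) = .00634.

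| School-level R² | 0 | .30 | .50 | .80 | .90 |
|---|---|---|---|---|---|
| ICC must be below | .0063 | .0091 | .0127 | .032 | .063 |

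**School-level R² needed for MDES = .10:**

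| ICC | .01 | .02 | .04 | .06 |
|---|---|---|---|---|
| Unlimited students, 22 schools | .37 | .68 | .84 | .89 |
| 600 per school, 22 schools | .48 | .74 | .87 | .91 |
| Unlimited students, 20 schools | .43 | .72 | .86 | .91 |

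**MDES at 600 students per school, student-level R² .30, 22 schools:**

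| ICC | R²_school 0 | .30 | .50 | .80 | .90 |
|---|---|---|---|---|---|
| .01 | .133 | .113 | .099 | .071 | .058 |
| .02 | .183 | .155 | .133 | .090 | .070 |
| .04 | .255 | .214 | .183 | .120 | .090 |
| .06 | .310 | .261 | .222 | .144 | .106 |

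**Sensitivity of the .00634 ceiling.** It is .00630 with one df spent on the site covariate, .0057 with 20 schools (M = 2.963) and .0082 with one-sided .05.

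**Benchmark only.** The ICCs that reproduce both .29 and .28 depend on where the 30% applies: .057–.059 (both levels), .039–.041 (student level only) or .049–.052 (school level only). Under these, unlimited students would bring the MDES down only to .233–.255. With one-sided .05 the ICCs are .055–.081 and the floors .247–.263. These figures come from enrolled Tier 3 students, so applying them to school-wide records is an assumption.

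**The case against.** The strongest reply is that no sum has been shown to be wrong. The inputs are unstated, and the grid itself falls below .10 at ICC .01 with school-level R² .50, at .02 with .80 and at .04 with .90. The 2018-19 academic records, the site covariate, the choice of demographically comparable classrooms and the repeated annual records could all absorb between-school variance. Expecting to need random intercepts does not mean a large ICC, and nothing is said about the residual ICC after adjustment. Some pages were not available to us, and the plan's pointer to a sample size given below may lead there. The analyses are also supplementary.

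Much of this stands. An MDES below .1 is possible, the random-intercept sentence is weak evidence about size, and the Tier 3 benchmark should carry little weight. But every route to .1 runs through the ICC and the school-level R², not through the number of students, which is the reason the plan gives. The ceiling already assumes unlimited students, so no sample size stated elsewhere could rescue that reasoning. The one R² that the plan does state, .30, would still need an ICC below about .009.

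The bound does not cover an analysis of teacher dose within Partnership schools. The Power considerations decline to give power for dose-response, and it is unclear whether that covers The Guide. This is a gap in detail, and the conclusion does not rest on it.

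**Conclusion.** The concern holds. As written, the claim rests on a reason that cannot produce it. With 22 schools the between-school contrast reaches an MDES below .10 only if ICC × (1 − school-level R²) is below about .0063, whatever the number of students. The text available gives no ICC, school-level R² or clustered calculation for this contrast. At 600 students per school and 30% of variance explained at both levels, the MDES runs from .113 to .261 for ICCs of .01 to .06.

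This assumes 80% power, two-sided .05 and a standardised mean difference; the alternatives tried move the ceiling only between .0057 and .0082. For absences and referrals, where the plan will "estimate models that include the Zero Inflated Poisson link function for count" outcomes, the values are only indicative. Primary intent-to-treat power and the target sample size are not affected.

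**What to change.** Withdraw the overpowered claim for the Partnership-versus-Wellness contrast. In its place give a clustered MDES that states the number of students, classrooms and schools, the ICC, R² at school and student level, and alpha, with a separate statement for count outcomes. Estimate the ICC and school-level R² from the school-wide records, from 2018-19 onward. Whether that baseline year exists for the two schools added later is not stated and should be checked. Until then, show a range that includes high school-level R² as well as 0 to .30, such as the grid above.

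It would also help to say whether the statement on dose-response power covers The Guide and, if it does not, to give the teacher-dose analysis its own power statement with numbers of teachers and classrooms.

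The cost is one restated sentence, one clarifying clause and an estimate from records the study already plans to collect. No design change is needed.

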*Model modifications for students receiving tier 3 services.* To evaluate the effects of the enhanced treatment on students who receive tier 3 clinical services, and to accommodate the fact that there will be a rolling admission into clinical services, the treatment parameter will be interacted with a dosage parameter measuring each individual student's weeks of treatment received. This interaction term will provide a treatment effect estimate that is calibrated by dosage, as measured by weeks of treatment received. Because we will use an active treatment, we will be able to detect treatment-by-dosage differences between the enhanced and control treatments. To accommodate the possibility that random assignment does not create exactly equal groups with K=22, and to provide interpretable estimates of change in response to the intervention, we will use difference scores as the dependent variable unit of analysis for students receiving tier 3 clinical services. This will facilitate the direct examination of how services received over time influences youth change. The null hypothesis associated with change scores is that baseline differences remain constant and there would thus be no mean change across measurement occasions. Rogosa and colleagues (58-60) highlight the utility of using difference scores to evaluate pretest-posttest change in similar studies, indicating that previous work critical of this approach has been misleading in that it focused on several restrictive assumptions including high correlations of pretest and posttest measures as well as equal variances across measures over time. Given our previous research, outcomes, and statistical model, we believe that difference scores are the appropriate dependent variable.

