Given the experiment will examine intent-to-treat effects in a real-world setting, we will conduct analyses to investigate variability in implementation and compliance to enhance causal effect interpretation of clients "as treated." Specifically, we will use a Bayesian Additive Regression Tree approach (BART; 61) to delineate the impact of key treatment assumptions (e.g., compliance, fidelity, etc.), as well as to estimate the impact of assumption violations on the estimation of causal effects in the design. BART is an extension of Classification and Regression Tree (CART) models that is based on a recursive partitioning algorithm that explains variation in the outcome through repeated splits of the data into homogenous subgroups that are similar on predictor variables. One significant strength of BART is that it is capable of handling a large number of predictors and incorporates higher-order interactions that may be excluded from parametric analysis. Research indicates that BART is insensitive to tuning parameters and produces more accurate estimates of treatment effects compared to other methods of analyzing treatment effect heterogeneity (i.e., propensity score matching, propensity-weighted estimators, instrumental variable procedures, and regression adjustment; 61). Note that this BART enhancement to the randomized, experimental design should not be mistaken for a Bayesian trial design.

*Power considerations.* The design originally included a planned sample size of approximately N=2800 (1400 per arm) for Aims 1 and 2. We previously revised power estimates for these study aims that consider the possibility of reduced participant involvement given COVID-19 and recruitment challenges more broadly, with a revised sample size of approximately N=1400 (700 per arm). With the research study period concluding in June 2023, we have revised the enrollment projection to a conservative estimate of N=1225. With our currently active sites (J=22) and the total number of students enrolled in the study (N=1225, including expected spring 2023 enrollment), assuming 30% of variance

PRINCIPAL INVESTIGATOR: [name]

explained in the primary outcomes by pre-test covariates, and 80% power, we have a minimum detectable effect size (MDES) of .29. If we reach our goal of 1400 students, we will be at .28.

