A priori power analyses indicate that we will be adequately powered to detect any primary outcome that has an effect size of  $d=.29$  or greater (i.e., between small [ $d=.2$ ] and medium [ $d=.5$ ] in size per Cohen, 1988). Statistical software does not differentiate between one variable (e.g., depression) or another (e.g., anxiety) when executing power analysis for an outcome. Notably, Ferguson (2009) recommends that "minimum effect size representing a 'practically' significant effect for social science data" with difference measures like Cohen's  $d$  is .41.

Variation in cluster size is a typical (and expected) occurrence in cluster-randomized trials, with a priori power analyses invoking the projected average sample size per cluster for projected MDES estimates to accommodate differences in cluster size. Moreover, methodological literature has shown that any negative influence of cluster imbalance is limited to situations where there is a severe Pareto imbalance, defined as "a situation in which 80% of the subjects actually belong to only 20% of the clusters" (Guittet, Ravaud, & Giraudeau, 2006). This is not the situation here, and thus we expect the observed imbalance to have a negligible impact on analyses. Power analysis for the study corresponds to the ITT effect of the intervention, wherein the probability of the intervention's ability to reject a null-hypothesis of no intervention effect is considered. Power estimates are not provided for the dose-response effect (i.e., the effect of treatment at varying dose levels) as this will be calculated using a Bayesian method (i.e., Bayesian Additive Regression Trees, BART).

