Estimating dose-response effects using a conventional, frequentist treatment\*dosage interaction would violate the strong ignorability assumption, confound effects with varying characteristics of participants and sites, and yield biased estimates (e.g., 69,70). The BART models proposed in the current application have demonstrated efficacy in estimating treatment effects in quasi-experimental studies that may vary as a function of a continuous variable, such as treatment dose (71). The BART approach will provide an estimate of the treatment effect for those who received the intervention conditional on baseline covariates (i.e., conditional treatment effect on treated). We will calculate conditional treatment effects on treatment for each individual following the Neyman-Rubin causal model (72,73). The BART models will yield an effect size for each varying level of exposure, as well as provide a credible interval (analogous to a frequentist confidence interval) for the effect estimate. The BART models will also allow missing data to be included as a feature in the predictive model using a "missingness incorporated in attributes" approach. This means that BART will use all available data. Kapleiner and Bleich (74) demonstrated that this approach is computationally efficient and that results are comparable to other advanced missing data approaches (e.g., multiple imputation).

We will conduct additional analyses to ensure the results from our original models are not due to random noise in the sample. Specifically, we will conduct 250 Monte Carlo simulations in which a random binomial variable will be generated to represent an instrumental variable such that it will be uncorrelated with covariates or outcomes. Then we will regress each of the outcomes on the binomial variable yielding a parameter representing the relationship between the instrumental and binomial variable that is unrelated to the outcomes. This analysis will test the sensitivity of our BART models on estimated treatment effects and determine how robust our credible intervals are.

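### The only model written specifically for Tier 3 outcomes estimates the treatment effect through an arm-by-weeks-received interaction, which the plan elsewhere calls biased and has not powered, so the primary Aim 2b estimate can be read two ways

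*Combined protocol and SAP*

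**What the plan says.** All of this is in the combined protocol and SAP.

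- **Analytic Plan, general model.** A two-level hierarchical linear model (HLM) has students within schools, site as a covariate and random school intercepts. It closes: "This general analytic framework will be used in aims 1 and 2. Details, exceptions, and modifications to it are discussed below".
- **Analytic Plan, model modifications for Tier 3 students.** To evaluate the enhanced treatment under rolling admission, "the treatment parameter will be interacted with a dosage parameter measuring each individual" student's weeks of treatment received. The text continues: "This interaction term will provide a treatment effect estimate that is calibrated by dosage". The dependent variable is a difference score.
- **Aim 2 measures.** Aim 2 is called primary. Aim 2b is its Tier 3 part, covering social and emotional/behavioral functioning.
- **ITT statements in the Analytic Plan.** "In addition to primary intent to treat analyses, we plan to use quasi-experimental methods to test dose-response" (in that sentence the dose-response work concerns The Guide curriculum), and "Given the experiment will examine intent-to-treat effects in a real-world setting".
- **Power considerations.** "Power analysis for the study corresponds to the ITT effect of the intervention". "Power estimates are not provided for the dose-response effect", because that effect is left to BART. The plan then says that a conventional frequentist treatment-by-dosage "interaction would violate the strong ignorability assumption, confound effects with varying characteristics of participants and sites, and yield biased estimates".
- **Conceptual Framework and Outcomes.** Partnership students are predicted to receive a higher dose and to stay in services longer.
- **Identifying eligible participants.** Students already in treatment may enrol. The Tier 3 paragraph does not say when weeks start to count.

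**The concern.** Two instructions for the same outcomes cannot both be followed. One section produces the Tier 3 treatment estimate from an arm-by-weeks interaction, and another rejects that kind of term as biased. The ITT statements and the MDES point to a third quantity, the plain arm contrast, which is not written out for Tier 3.

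The choice affects the answer to a primary sub-aim. The decision question is whether adding Partnership improves outcomes, whereas the interaction asks whether the arm difference changes with weeks received. Because weeks received is partly a consequence of arm, conditioning on it gives up the protection of randomisation. With the text as it stands, an analyst could defend either estimate after seeing the data.

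**Working it through.** **1. The plan's own figure.** Inputs from Power considerations are 22 schools, N = 1225, 30% of variance explained by covariates, 80% power and MDES .29 (.28 at N = 1400). The ICC and alpha are not stated; I assume two-sided .05.

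MDES = M × √[4·ICC·(1−R²_school)/22 + 4·(1−ICC)·(1−R²_student)/N], with M = t(.975, 20 df) + t(.80, 20 df) = 2.086 + 0.860 = 2.946.

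With R² = .30 at both levels and ICC = .059, the bracket is .0075 + .0022 = .0097, its root is .098, and 2.946 × .098 = .29. If R² applies at student level only, the ICC needed is .041; at school level only, about .052. The same ICCs give .284 to .286 at N = 1400, compatible with .28 once rounding of .29 is allowed for. So .29 is attainable, though not verifiable, and it belongs to the arm contrast in SD units. An interaction is in SD per week, so .29 does not carry over to it.

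**2. What each coefficient estimates.** Write change = a + b·Arm + c·Weeks + d·Arm×Weeks + school + error.

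- d is the change in the arm difference per extra week. If Partnership adds .29 SD at every number of weeks, d = 0.
- b is the arm difference at one value of weeks (zero, or the centring value), among students grouped by something arm can change. It is not the ITT effect.

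**3. Illustration with no true effect.** All inputs here are assumed: mean weeks 20 in Wellness and 24 in Partnership, SD 10, outcome SD 1, and correlation r of weeks with improvement −.30 in Wellness.

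- Same r in Partnership: d = (−.30 + .30)/10 = 0, but b = .30 × 4/10 = +.12 SD although nothing works.
- Partnership r of −.25, −.20 or −.15: d = (r_Partnership + .30)/10 = .005, .010 or .015 SD per week.

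**4. Illustration of power with a true average effect of .29.** Assumed: mean 20 weeks in both arms, SD 10 or 6, ICC .059. Within-school residual variance is .70 × .941 = .659. SE(d) = √[4 × .659/(1225 × SD²)] = .0046 (SD 10) or .0077 (SD 6). Power ≈ Φ(d/SE − 1.96), plus the opposite tail where it matters.

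| Shape of effect | d per week | SD 10 | SD 6 |
|---|---|---|---|
| Equal at all weeks | 0 | 5% | 5% |
| Half proportional to weeks | .145/20 = .00725 | 35% | 16% |
| Wholly proportional | .29/20 = .0145 | 88% | 47% |

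Simulation of 3,000 trials per case gave 5%, 34%/16% and 87%/46%, with about 80% for the arm contrast in the equal-effect case. The interaction's power therefore ranges from the error rate to slightly above that of the arm contrast, depending on a shape and spread that the documents do not give.

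**5. Rolling admission.** This is the plan's stated reason for the interaction. It concerns when a student enters. Weeks received also depends on when treatment ends, which can follow severity and progress. Differing entry times therefore do not require conditioning on weeks received.

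**The case against.** The Tier 3 paragraph offers a dosage-calibrated estimate. It does not call that estimate primary and does not name Aim 2b. The general model covers both aims, the analyses are described as ITT, and the power section moves dose-response to BART. On this view the interaction sentence is a leftover or a supplementary analysis, and nothing has been displaced. Also, if weeks mainly tracked elapsed time, an effect growing with weeks would be natural and the interaction could perform well.

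Much of this stands. A reader might infer that the plan has made the interaction its primary Aim 2b analysis, or has abandoned ITT; the wording supports neither. A reader might also take the ITT sentence that mentions dose-response as a statement about weeks of Tier 3 treatment, but it concerns The Guide. Non-zero interactions under no effect need the weeks-outcome correlation to differ by arm, and nothing in the documents shows that it does.

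What does not stand is that the text resolves itself. The Tier 3 paragraph is the only HLM specification particular to these outcomes, it is introduced as the way to evaluate the enhanced treatment, and nothing marks it as superseded or secondary. Keeping the arm term in that model does not rescue the ITT effect, for the reason in step 2 of the working.

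**Conclusion.** The inconsistency is explicit and should be settled before analysis, because it leaves the primary estimate of a primary sub-aim open to two readings, and the one written out for Tier 3 is of a kind the plan itself rejects. This conclusion rests on the text alone and on no simulated figure.

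Its numerical size is unknown. The documents give no mean, SD or arm difference for weeks and no correlation of weeks with outcome. The +.12 SD, the .005 to .015 SD per week and the power range of 5% to 88% show what can happen under assumed inputs. They are not estimates for this trial, and a reader should not infer that the Tier 3 result will be biased by any such amount.

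**What to change.** Reconcile the Tier 3 model paragraph with Power considerations:

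1. Remove weeks received and its interaction with arm from the primary Tier 3 HLM.
2. State that the primary Aim 2b estimate is the randomised-arm effect from the general two-level model (site covariate, random school intercept), fitted to the Tier 3 change outcomes already defined. This is the effect to which the .29 refers.
3. Keep weeks-received dose-response only in the BART analysis, labelled exploratory and dependent on no unmeasured confounding of dose.
4. State when weeks start to count for students already in treatment at enrolment.

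The cost is text only, with no new data; the HLM dose-response estimate is lost. A joint longitudinal model of all intake, three-monthly and closure assessments could be added as an optional sensitivity analysis. It is not part of the required change: it would replace the difference scores that the plan justifies at length, and it relies on data being missing at random after case closure.
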